Energy Expenditure of Remote Exercise Sessions (optional). Energy expenditure of the remote sessions will be assessed in a volunteer sample using a previously validated portable, open-circuit indirect calorimeter (Cosmed, Italy) which measures breath-by-breath ventilation, expired oxygen, and carbon dioxide. The flow turbine will be calibrated using a 3.0-L syringe. The lightweight (~1.5 kg) portable system will be attached by a harness around the waist and shoulders of the participant before each assessment. During exercise sessions, participants will breathe into a facemask that directs air into the unit housing the O₂ and CO₂ analyzers. Data will be retrieved for analysis via a serial port interface and software provided with the calorimeter, and aggregated over 20-second epochs for the calculation of 1-min averages. MET levels will be age corrected using the Schofield equation (88) as recommended by McMurray et al (89). Participants will be asked to wear wrist ActiGraphs during the assessment for comparison of physical activity levels between devices.

SAMPLE SIZE, STATISTICAL METHODS, AND POWER CALCULATION

Power/sample size. The mean 6 mo. weight loss in our completed trial in adults with MRDs, using a protocol similar to the *IH* arm in the proposed trial, i.e., eSLD and behavioral counseling delivered by monthly home visits, was 5.5 kg (58). This does not reach the 8.5 kg (~5%) average 6 mo. weight loss defined as clinically meaningful by current weight management guidelines (53). We expect 6 mo. weight loss in the *GR* arm, which includes weekly group counseling and group exercise, will reach or exceed 8.5 kg. To detect a clinically meaningful difference of 3 kg (133, 176-180) in 6 mos. weight loss between the *IH* and *GR* arms, with 80% power and a type 1 error rate of 0.05, assuming a common standard deviation of 6 kg, will require 64 participants/group. Secondarily, we will have 70% power to detect a 3 kg difference in a completer analysis with an attrition rate of 20%; however, we expect attrition will be lower based on experience (71, 78, 181), and our use of retention/incentive strategies to minimize loss to follow-up. Thus, a sample of 64/group will provide adequate power for both our primary intent-to-treat analysis with imputed missing data (power = 80%) and our secondary completer only analysis (70%).

Analysis plans. *Primary aim* will use a 2-sample independent t-test to compare 6 mo. weight loss between the 2 intervention arms in both an intent-to-treat, and completer only analysis. Procedures for handling missing data are described below. We will examine the impact of baseline characteristics (age, sex, race/ethnicity, weight, type of MRD, wheelchair use, employment status, living situation, food shopping and preparation) on weight change using linear regression controlling for treatment. We will examine the main effects of each of these variables, as well as the potential interaction effect with treatment.

Secondary aim 1, a comparison of 18 mo. weight loss, will mirror the analysis for the primary aim. We will use a 2-sample t-test to compare weight change (0-18 mos.) between the 2 intervention arms. Mixed linear models will be used to compare weight change from 0-18 mos.

between intervention arms controlling for intervention arm and baseline weight. We anticipate greater loss to follow-up over time; however, we expect data to be missing at random. Under this assumption, mixed linear models will provide unbiased treatment comparisons. We will assume an autoregressive correlation structure of the dependent variable (weight) over time, and evaluate the potential for time-by-treatment interactions.

Secondary aim 2, a between arm comparison of the proportion of participants achieving $\geq 5\%$ weight loss (0-18 mos.) will be evaluated using a chi-square test. Participants without an 18 mo. weight will be classified as not meeting the $\geq 5\%$ weight loss goal. We will also examine the impact of baseline characteristics, as previously defined, on 18 mo. weight loss using logistic regression.

Secondary aims 3 and 4, between arm comparison of change in risk factors and quality of life (0-6 and 0-18 mos.) will be evaluated using a 2-sample t-test.

Exploratory aims will examine the influence of the following on weight loss at 6 mos.: behavioral session attendance, compliance with the recommendations for diet (energy intake, number of meals/shakes, servings of fruits/vegetables), PA (min of moderate-vigorous PA, min sedentary time), self-monitoring of diet and PA, sleep, and medications assessed over the time period of interest, i.e. (0-6 and 0-18 mos.) and the change in self-efficacy for PA and dietary change, dietary self-regulation, social support for diet/PA, and barriers to PA from 0-6 mos. We will examine the influence of these factors as covariates, in addition to treatment, on weight loss at 6 mos. As we have 128 observations with a rule of thumb of at least 30 observations for each variable in the model, judicious model selection will be completed as we can only expect to identify ~ 4 variables that are related to weight loss in a single model. First, we will assess if these variables differ by treatment at the 0.10 level and if they do they will be considered for future modeling. If in a two-factor model, the variable and treatment have a potential interaction at the 0.10 level that interaction will be considered for future modeling. Subsequently, the main effects and interaction effects along with treatment will be examined in a joint model. Given the pitfalls of forward and backward selection, we will utilize best subsets criteria based upon Mallow's Cp statistic to produce the most parsimonious and least biased model of weight loss at 6 months. This should allow us to identify what variables most highly influence our outcome along with treatment and/or the mechanism(s) of action that are impacting weight loss. We will do the same for weight loss at 18 months, as this measure may have similar or different variables that impact this long-term outcome.

Missing Data/ imputation. All analyses will be based on intent-to-treat principles and missing data for analyses of the primary aim will be imputed; therefore, oversampling for attrition is not needed. We will determine if the proportion of participants lost to follow-up differs by treatment. If so, we will determine if there are differences in demographic characteristics (sex, age, baseline weight, $p < 0.05$) between completers and those lost to follow-up. If missing data are related to treatment and/or these demographic characteristics, we will use model based multiple imputation; otherwise, we will use traditional multiple imputation. Statistical analysis will be completed with SAS version 9.4 or higher.

REFERENCES

2. Brault MW. Americans with Disabilities: 2010 Current Population Reports. Washington, DC: US Census Bureau; 2012. p. 40-131.

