Official Title: Weight Management for Adults with Mobility Related Disabilities

NCT Number: 04046471

Approval Date: January 26, 2024

Document: Study Protocol with Statistical Analysis Plan

AIMS AND HYPOTHESES

Individuals with mobility related disabilities (MRDs) represent a sizeable and growing segment of the U.S. adult population, with high rates of obesity, and limited options for successful weight management. Obesity in adults with MRDs increases the risk of chronic disease, and may limit the ability to ambulate, either with or without assistive devices (wheelchair, cane etc.), perform transfers (wheelchair users), increase the risk for pressure sores, respiratory problems, carpal tunnel syndrome, and interfere with self-care, and reduce participation in daily activities. Adults with MRDs face numerous barriers to participation in traditional weight management programs including the lack of affordable, accessible transportation to attend on-site meetings or engage in physical activity (PA), lack of accessible recreational facilities with accessible fitness equipment, and difficulty with food shopping and meal preparation. The 2005 Surgeon General's Call to Action to Improve the Health and Wellness of Persons with Disabilities, and numerous subsequent government sponsored reports, have highlighted the need for accessible health promotion efforts to reduce health disparities between adults with and without MRDs. However, a limited number of intervention strategies, specific to weight management in adults with MRDs, have been developed and evaluated. As described in this proposal, our group has evaluated an enhanced version of the Stop Light Diet (eSLD = SLD+portion-controlled meals and low calorie shakes) for weight management in a sample of 126 adults with MRDs. The eSLD simplifies meal planning, food shopping and meal preparation. When prescribed in conjunction with a monthly behavioral intervention, delivered in an individual home visit format, the eSLD resulted in significantly greater weight loss when compared with a conventional meal plan diet at 6 mos. (eSLD = -4.1%, meal plan = -2.3%, $p=0.02$) and 12 mos. (eSLD = -6.2%, meal plan = -0.6%, $p=0.005$). Although these results are encouraging, alternative strategies to improve outcomes and to deliver weight management to larger numbers of adults with MRDs in a cost-effective manner, are warranted. Thus, the proposed two-arm randomized trial will compare weight loss (6 mos.) and maintenance (18 mos.) between an individual home visit intervention (*IH*), using an enhanced version of the protocol used in our previous trial, and an intervention delivered remotely via video conferencing to groups of overweight/obese adults with MRDs in their homes (*GR*). Both interventions will be delivered in a format that eliminates the transportation barrier, prescribed an eSLD, and will self-monitor body weight using electronic scales. The *GR arm* will include group behavioral counseling and group PA delivered remotely via video conferencing (Zoom™ software) on a tablet computer (iPad mini) to participants in their homes, and use commercially available web-based applications for self-monitoring/participant feedback for diet (Lose It! software) and PA (Fitbit activity tracker). This approach reduces barriers to both behavioral session attendance and PA, provides timely feedback relative to diet and PA, and promotes interaction and support in a group who are often socially isolated. The *IH arm*, which represents a modified version of the protocol used in our previous trial, will include behavioral counseling delivered during individual home visits, a prescription for self-directed PA, and self-monitoring of diet and PA using conventional paper and pencil self-reports. Both groups will receive identical attention with 2 interventions having the potential for clinically meaningful weight loss, i.e., $\geq 5\%$. This trial will address the following primary, secondary and exploratory aims.

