
Primary aim: To compare mean weight loss between the *GR* and *IH* arms across 6 mos. We expect significantly greater weight loss in the *GR* compared to the *IH* arm.

Secondary aims. *To compare the GR and IH arms on the following:* 1) Mean weight loss (0-18 mos.); 2) The proportion of participants who achieve clinically significant weight loss ($\geq 5\%$ from baseline) at 18 mos.; 3) Changes in cardiovascular disease risk factors (blood pressure, total, HDL and LDL cholesterol, triglycerides, HbA1c for diabetics, waist circumference) from 0-6 and 0-18 mos.; 4) Changes in quality of life from 0-6 and 0-18 mos. We expect more favorable changes in all secondary outcomes in the GR compared with the IH arms. 5) Cost and contingent valuation analysis to compare costs between the GR and IH arms. Based on our experience with remote delivery for weight management using both group phone (DK76063) and virtual reality formats (DK94833), we expect GR to be less expensive than the IH arm.

Exploratory aims. *Initial weight loss is highly predictive of longer-term weight loss; therefore, we will examine the influence of the following variables on weight loss at 6 and 18 mos.:* behavioral session attendance, compliance with the recommendations for diet (energy intake, number of meals /shakes, servings of fruits/vegetables), PA (min of moderate-vigorous PA, min sedentary time), and self-monitoring of diet and PA, self-efficacy for dietary change and PA, dietary self-regulation, social support for diet/PA, barriers to PA, sleep, and medications.

BACKGROUND/SIGNIFICANCE

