We propose a 2-arm randomized trial (group remote (*GR*) vs. individual home visit (*IH*)) using intent-to-treat principles, to compare body weight following weight loss (6 mos.) and maintenance (18 mos.) in overweight/obese adults with MRDs. interventions will be delivered by trained health educators and will include behavioral sessions, a reduced energy diet (eSLD), increased PA, and self-monitoring of weight using electronic scales. The *GR* arm will be delivered via video conferencing (Zoom™ software) on a tablet computer (iPad mini) with self-monitoring of diet and PA using commercially available technologies. Participants in the *IH* arm will self-monitor diet and PA using paper and pencil records. Due to COVID-19, all Cohort 1 *IH* intervention meetings will be held by phone per CDC social distancing recommendations. Participants are asked to send pictures of the tracking sheets to the health educator prior to the phone meeting. The primary outcome (weight) will be assessed during home visits at baseline (mo. 0), following weight loss (6 mos.), during (12 mos.) and at the end of maintenance (18 mos.). Our group has experience with all proposed intervention components and outcome assessments from previously completed (44, 58, 71, 78, 88, 89) or on-going trials (DK83589, HD79642). The following design attributes, described in detail subsequently, ensure the scientific rigor of the proposed trial: 1) Randomized design with equal allocation to groups, with allocation assignment concealed. 2) Adequate statistical power to address the primary aim. 3) Strategies to ensure the recruitment of sufficient participants to achieve our desired sample size. 4) Retention/incentive strategies to reduce loss to follow-up. 5) Controlling for attention by maintaining equal contact in both groups. 6) Secondary/exploratory aims to maximize the use of data, e.g., analysis to examine the impact of process variables/participant characteristics on

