Orientation. Health educators will conduct home visits (~90 min) with all participants prior to initiating the intervention to provide a detailed description of both the dietary (eSLD) and PA components of the intervention and delivery formats (remote or home visit). All participants will be provided with an iPad mini tablet computer and electronic wireless scales. Access to non-study related materials, e.g., web browsing, app store etc., will be blocked on all iPads until completion of the study. iPads for the *GR* arm will be pre-loaded with the video conferencing (Zoom™ software), the Lose It! and Fitbit applications, and behavioral session materials (described later). Participants in the *IH* arm will be provided with hard copies of the intervention materials and will be shown how to self-monitor diet and PA using hard copy records. During orientation, both intervention arms will receive a tutorial on the use of the iPad and electronic scales, and procedures for making digital photographs of meals, to be used in the assessment of dietary intake (described in assessment section). Participants in the *GR* arm will be oriented to the video conferencing software and both the Lose it! and Fitbit apps/devices used for self-monitoring diet and PA. Time will be allotted for practice and questions. Per inclusion/exclusion criteria, those unable to perform these tasks will be ineligible. Tutorials describing trouble shooting for common technical problems, e.g., internet connectivity, data entry using Fitbit, Lose It!, will be loaded on the iPad. Technical issues can also be resolved during behavioral sessions, or by contacting research staff by phone or email. The *GR* arm will be provided with an HDMI adaptor allowing video conference sessions to be displayed on a larger TV screen, if desired. Reminders regarding upcoming behavioral/PA sessions etc., or to prompt participants in the *GR* arm who are non-compliant with the study protocol, will be sent via the iPad.

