Behavioral session/frequency/duration (Table 1). GR arm. Behavioral sessions (10-15 individuals) will be conducted using video conferencing (Zoom™ software) 2/mo. during weight loss and the first 6 mos. of maintenance (mos. 0-12), and 1/mo. during the last 6 mos. of maintenance (mos. 13-18). *IH arm.* Behavioral sessions will be conducted with individual participants during home visits. Behavioral sessions in the IH arm will follow the same frequency as the GR arm and will occur 2/mo. during weight loss and the first 6 mos. of maintenance (mos. 0-12), and 1/mo. during the last 6 mos. of maintenance (mos. 13-18). Meeting duration will be 45-60 min. for both groups across the intervention. Due to COVID-19, all Cohort 1 IH intervention meetings will be held by phone per CDC social distancing recommendations. Participants are asked to send pictures of the tracking sheets to the health educator prior to the phone meeting

Behavioral session content-weight loss. Behavioral sessions will be identical between groups and will include a review of participants self-monitored data for diet, PA, and weight recorded since the previous session, a question to generate discussion regarding diet and PA, a lesson on a weight management topic, and an experiential learning assignment requiring problem solving or the practice of behavioral strategies, to be completed prior to the next session. Lessons will also include topics such as cost and time efficient strategies for food shopping and

preparation, specific strategies for increasing daily PA and decreasing sedentary time, and maintaining adequate hydration, eating away from home etc., with examples and discussion questions specific to individuals with MRDs.

Behavioral session content-weight maintenance. Behavioral sessions during maintenance will focus on planning and following a meal plan diet, with or without incorporation of PCMs, and cardinal behaviors for successful weight maintenance, such as self-monitoring, regular PA, eating on weekends/vacations, and controlling energy intake on special occasions and holidays, etc.

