PA delivery. *Participants in the GR arm* will be asked to attend 30-min group exercise sessions conducted using video conferencing (Zoom™ software) 2 x/wk. during weight loss (0-6 mos.) and 1x/wk. during maintenance (7-18 mos.) Exercise sessions will be conducted in conjunction with behavioral sessions when schedules coincide. In such cases the total session time (behavioral+exercise) will not exceed 60 min. Group sessions will include a warm-up, 20 min. of moderate intensity aerobic activity, 10 min of RT, and stretching and cool-down. Exercise sessions will include individuals with a range of functional abilities, e.g., wheelchair users/ambulatory. [name], an adapted PA specialist, will modify activities, as necessary, to insure they are applicable for all participants. Our trial in adolescents with IDD demonstrated the feasibility of the home-based group video conference approach for delivering exercise to groups varying widely in physical abilities (preliminary studies). Group sessions will provide 40 minutes of the 150 min./wk. recommendation for aerobic activity. To assist participants in both study

arms in meeting the 150 min./wk. goal, all group sessions will be video recorded and uploaded remotely to participant's iPads where they can be accessed for use at any time. In addition, information regarding exercise resources available from the National Center on Health, Physical Activity and Disability, Craig Hospital, and the Christopher and Dana Reeve Foundation will be pre-loaded on the iPad of participants in all study groups. *The IH arm* will be asked to complete the exercise recommendations on their own, as is customary in standard care weight management. Participants in the *IH* arm will receive brief (5-10 mins.) support/problem solving phone calls (1x/wk.) and iMessages (1x/wk) from the health educator an approach that has been shown to increase exercise in adults with MRDs (44).

OUTCOME MEASURES

Weight/Height: Ambulatory participants. Weight will be measured in duplicate with a portable, calibrated digital scale. (Model #PS6600, Befour, Saukville, WI.). Standing height will be measured in duplicate with a portable stadiometer (Model #IP0955, Invicta Plastics Limited, Leicester, UK).

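### The protocol claims identical attention and equal contact, but live exercise contact is not matched: about 320-380 scheduled live min/mo. in GR against 112-163 in IH over months 0-6

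*Combined protocol and SAP*

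**What the plan says.** Two places in the combined protocol and SAP make the claim. Aims and Hypotheses states "Both groups will receive identical attention with 2 interventions having the potential for clinically meaningful weight loss". Study Type and Design lists "Controlling for attention by maintaining equal contact in both groups" among the attributes that are said to ensure rigor. Neither statement is limited to counselling.

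Intervention Description sets the schedule:

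- **Orientation, both arms:** "Health educators will conduct home visits (~90 min) with all participants prior to initiating the intervention".
- **Counselling, GR:** "Behavioral sessions (10-15 individuals) will be conducted using video conferencing", twice a month to month 12 and monthly in months 13-18.
- **Counselling, IH:** "Behavioral sessions in the IH arm will follow the same frequency as the GR arm and will occur 2/mo. during weight loss". It is delivered individually, and by phone for Cohort 1 because of COVID-19.
- **Counselling length:** "Meeting duration will be 45-60 min. for both groups across the intervention".
- **Exercise, GR:** participants "will be asked to attend 30-min group exercise sessions conducted using video conferencing", twice a week in months 0-6 and once a week in months 7-18. A session may be joined to a counselling session, and the joint meeting may not exceed 60 min.
- **Exercise, IH:** self-directed, with one 5-10 min support call and one iMessage a week.

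The Orientation paragraph also says that reminders, and prompts to GR participants who are not complying, go out through the iPad.

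**The concern.** Counselling and orientation are largely matched, but the weekly exercise support is not. GR gets an hour of live group exercise a week in the window of the primary endpoint, while IH gets a short call and a message. If GR loses more weight, a reader who relies on the two statements would rule out extra live contact as an explanation. The schedule does not allow that.

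The imbalance also has no single direction. A GR participant spends more live time in the programme, while an IH participant receives more staff time per head. The word equal hides both facts.

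**Working it through.** **The plan's own figure.** The only contact-time total stated is the aerobic time from GR sessions in months 0-6, in PA delivery: 2 sessions/wk × 20 min = 40 min/wk. It reproduces.

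**Inputs.** Counselling of 45-60 min, 2/mo. to month 12, then 1/mo.; GR exercise of 30 min, 2/wk then 1/wk; IH calls of 5-10 min, 1/wk; 60-min cap on joint GR meetings. Assumed: 52/12 = 4.33 weeks/mo., full attendance, and IH calls and messages continuing to month 18 (no end date is given). Cohort 1 phone meetings count as live minutes.

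**Participant live minutes per month, months 0-6.**

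- GR, separate sessions: 2 × 45 + 8.67 × 30 = 350, to 2 × 60 + 8.67 × 30 = 380.
- GR, both counselling sessions joined to exercise at the cap: 2 × 60 + 6.67 × 30 = 320. Each joint meeting then has 60 − 30 = 30 min for counselling, against 45-60 in IH.
- IH: 2 × 45 + 4.33 × 5 = 112, to 2 × 60 + 4.33 × 10 = 163.
- Ratios at equal nominal counselling length: 350/112 = 3.1; 380/163 = 2.3; joint meetings 320/163 = 2.0.

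With 4-week months the ranges are 300-360 and 110-160. If joint meetings ran only 45 min, GR would be 2 × 45 + 200 = 290, still above the IH range.

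The same formulas by phase:

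| Months | GR separate | GR joint | IH | Ratio, equal nominal length |
|---|---|---|---|---|
| 0-6 | 350-380 | 320 | 112-163 | 2.0-3.1 |
| 7-12 | 220-250 | 190 | 112-163 | 1.2-2.0 |
| 13-18 | 175-190 | 160 | 67-103 | 1.5-2.6 |

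**Staff minutes per participant, months 0-6.** GR live minutes are divided by group size. The plan gives 10-15 for counselling only, so the same size is assumed for exercise. GR: 320/15 = 21 to 380/10 = 38. IH: 112-163. This is staff time per head before travel. It is not one-to-one time, since GR sessions are shared.

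**Number of contacts per month.**

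| Months | GR separate | GR joint | IH live | IH live + iMessages |
|---|---|---|---|---|
| 0-6 | 10.7 | 8.7 | 6.3 | 10.7 |
| 7-12 | 6.3 | 4.3 | 6.3 | 10.7 |
| 13-18 | 5.3 | 4.3 | 5.3 | 9.7 |

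GR iPad prompts are left out because no frequency is given. With messages counted, the arms match only in months 0-6. With live contacts only, they match only from month 7. Both matches need separate GR sessions.

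**Related wording under Power/sample size.**

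- GR counselling is called weekly there but is 2/mo. in the schedule.
- The 8.5 kg loss is labelled about 5%. That needs a mean weight of 8.5/0.05 = 170 kg, which is 94% of the entry limit of 400 lb (181 kg).
- If the earlier trial's 5.5 kg loss and the 4.1% loss in Background describe the same group, its mean weight was 5.5/0.041 = 134 kg, and 8.5/134 = 6.3%.
- The sample size does not use this label. A t-test with 64 per arm, 3 kg and SD 6 kg has power 0.80.

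**The case against.** The best defence is that contact was matched by number. In months 0-6 one call plus one iMessage a week mirrors two exercise sessions a week, giving 10.7 a month in each arm. This may well be what was intended. It holds only if a text message equals a 30-min live session, GR iPad prompts are ignored and no GR sessions are joined, and the rule fails after month 6.

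A second defence is that live exercise is the treatment and not attention. It makes up 260/380 = 68% to 260/350 = 74% of GR minutes when sessions are separate. It is indeed an intended part of the GR package. But neither statement excludes it, and group exercise led live is also contact.

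Third, contact is not defined in the available text, and the Table 1 cited for counselling is not in it and might define the term. This stands as a caution. The case against the promise of identical attention is therefore firmer than the case against equal contact, and one should not infer that every possible definition of contact is breached.

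A reader might also infer that the primary comparison is biased or invalid. The documents do not support that. The aim begins "Primary aim: To compare mean weight loss between the" and names the two arms, so it compares packages, and differing content is part of the question. Nor do they support saying that GR simply receives more attention, since staff time per head runs the other way. The figures are scheduled minutes and say nothing about attendance.

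The exploratory models do not close the gap. They name behavioral session attendance and activity minutes, but not exercise-session attendance or call time.

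**Conclusion.** The two statements claim a property that the schedule lacks. In months 0-6 the ranges of scheduled live time do not overlap, which comes to 32-38 hours in GR against 11-16 in IH over the six months. That gap rests on 4.33 weeks/mo. and full attendance. The reversed staff figure also needs exercise groups of 10-15, and the later-phase figures need IH calls to continue to month 18.

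It would be too generous to call counselling fully matched, because the 60-min cap shortens it for GR whenever sessions are joined. It would be too strong to say that the trial's result is compromised: the primary test, its target difference, the sample size and the power all stand. The consequence is interpretive. A GR advantage could not be separated from extra live contact.

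The 6.3% figure is conditional and describes the earlier trial's group, not this trial's baseline. It is a labelling matter and adds nothing to the attention point.

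**What to change.** Replace the statements in Aims and Hypotheses and in Study Type and Design with: *Counselling frequency and planned session length are the same in both arms, except that GR counselling is shorter when combined with exercise (60-min cap); live exercise contact is not matched between arms.* Make no claim that attention was controlled when interpreting GR against IH.

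Report planned contact minutes by arm. Report delivered minutes, as participant time and as staff time, as far as the records allow. The sources are the time studies and participant-time survey planned under Cost analysis, and the attendance records. The plan does not show that call minutes or exercise-session attendance are logged, so the delivered figures may be partial unless such a log is added.

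Under Power/sample size, change weekly counselling to 2/mo., and remove or recheck the 5% label on 8.5 kg.

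The cost is wording in three sections and one descriptive table, with a narrower claim about why an arm won. No participants, visits or change to the intervention schedule are needed.
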